5.2 PATIENT DISPOSITION

Enrollment and reasons for discontinuation from the study will be summarized by treatment arm for the ITT population. Study treatment administration and reasons for

discontinuation from study treatment will be summarized for the safety-evaluable population.

5.3 PRIMARY ENDPOINT ANALYSIS

5.3.1 Definition of Primary Endpoint

The primary efficacy endpoint is investigator-assessed DFS, defined as the time from randomization to death from any cause or the first documented recurrence assessed by investigator, whichever occurs first. Recurrence is defined as any of the following (as assessed by radiologic recurrence criteria described in the study protocol): local recurrence of RCC, new primary RCC, and distant metastasis of RCC.

Data for patients without an investigator-assessed event will be censored at the last date the patient was assessed to be alive and investigator-assessed recurrence free (or, for patients with no post baseline disease assessment, at the randomization date).

5.3.2 Main Analytical Approach for Primary Endpoint

The statistical hypothesis which will be tested for investigator-assessed DFS is given in Section 2. Investigator-assessed DFS will be compared between treatment arms using the stratified log-rank test. The HR for recurrence or death will be estimated using a stratified Cox proportional hazards model, and the 95% CI for the HR will be provided.

The stratified analysis will use the same factors as the randomization stratification factors. The stratification factors will be obtained from the IxRS. If there is at least one stratum with less than 20 events, the geographic region will be removed as a factor in the model given its limited prognostic significance. After removing the geographic region, if there is still at least one stratum with less than 20 events, the stratification factor that contains the level with the smallest number of patients will be removed from the stratified analysis.

Results from an unstratified analysis will also be provided.

Kaplan-Meier methodology will be used to estimate for each treatment arm the investigator-assessed DFS rate at specific timepoints (e.g., every 6 months or yearly), and to estimate median DFS; Kaplan-Meier curves will be produced. Brookmeyer-Crowley methodology ([Brookmeyer and Crowley 1982](#)) will be used to construct the 95% CI for the median DFS for each treatment arm.

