Nephrectomy and/or metastasectomy tumor specimens from patients who meet eligibility criteria will be evaluated for PD-L1 expression. Patients must have sufficient amounts of viable tumor for IHC scoring of PD-L1 by the central pathology laboratory in order to be eligible. When tissue from both nephrectomy and metastatic specimens are available, submission of both specimens is recommended. The highest PD-L1 staining score will be used for patients who provide both nephrectomy and metastasectomy specimens.

Approximately 764 patients at high risk for RCC recurrence [see below for high-risk definition] will be randomized to one of the following arms in a 1:1 ratio:

- Arm A (experimental arm): Atezolizumab 1200 mg every 3 weeks (q3w) for 16 cycles or 1 year (whichever occurs first)
- Arm B (control arm): Placebo q3w for 16 cycles or 1 year (whichever occurs first)

High-risk patients are defined as patients with any of the following:

- T2 Grade 4, T3a Grade 3–4, T3b/c any Grade, T4 any Grade, TxN+ any Grade
- Limited metachronous/synchronous recurrence in patients who undergo complete R0 resection of all sites of disease. These patients will be eligible regardless of their original TNM/grade.

Number of Patients

A total of approximately 764 patients will be enrolled at approximately 215 centers globally.

Target Population

Inclusion Criteria

Patients must meet the following criteria for study entry:

- Signed Informed Consent Form
- Age \geq 18 years
- Eastern Cooperative Oncology Group (ECOG) performance status of \leq 1
- Able to comply with the study protocol, in the investigator's judgment
- Pathologically confirmed RCC with a component of either clear cell histology or sarcomatoid histology (sarcomatoid differentiation regardless of the primary epithelial subtype) that has not been previously treated in the adjuvant or neoadjuvant setting

Patients with localized disease with T2 Grade 4, T3a Grade 3–4, T3b/c any grade, T4 any grade and TxN+ any grade are eligible.

Patients with pulmonary (treated with sub-lobar or lobar resection), lymph node, or soft-tissue metachronous recurrence of disease occurring greater than 12 months following nephrectomy who undergo complete resection (R0; microscopically margin-negative resection in which no gross of microscopic disease remains) and have no evidence of disease following metastasectomy are eligible. Patients with resected CNS, bone, or adrenal metastasis are not eligible.

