3.3.2 Rationale for Patient Population

This study will enroll patients with RCC who are at high risk for disease recurrence following resection. The study will enroll patients irrespective of PD-L1 expression, (i.e., IC score of 0, 1, 2, or 3) as determined by IHC.

There is currently no widely accepted, effective adjuvant treatment for RCC, despite the recent approval of sunitinib in the United States. Advanced or metastatic RCC can be treated successfully with immune therapy and targeted therapy; however, such treatments have either not yet demonstrated efficacy or demonstrated limited efficacy in the adjuvant setting, and such approved therapies are associated with significant toxicities (e.g., diarrhea, rash, fatigue, hand-foot syndrome) that negatively affect quality of life. Further, the 5-year relapse rate for high-risk early-stage RCC is 30%–40% (Escudier et al. 2014). Therefore, there is a need for an efficacious, well-tolerated treatment for patients with RCC in the adjuvant setting.

[figure not shown]
3.3.2.1 Inclusion of Patients Who are at High Risk of Renal Cell Carcinoma Recurrence

This study will enroll patients who are classified as being at high risk of RCC recurrence with use of a TNM/grading system whereby high risk is defined as T2 Grade 4, T3a Grade 3–4, T3b/c any Grade, T4 any Grade, or TxN+ any Grade in order to define a population that is at the greatest risk of recurrence and most likely to benefit from adjuvant atezolizumab therapy.

Both tumor grade and stage are associated with RCC survival and recurrence (Zisman et al. 2001, 2002; Lam et al. 2005). In an Italian study of 338 patients with T3 and T4 tumors, grade was strongly associated with RCC-specific survival. Five-year RCC survival was 69.9%, 73%, 43%, and 31% for Grades 1, 2, 3, and 4 respectively (Ficarra et al 2007). Grade was also strongly associated with RCC-specific survival for patients with T2 tumors. In a small study of 39 patients with T2 disease, those with Grade 3–4 tumors performed substantially worse than those with Grade 1–2 tumors (Minervini et al. 2002). Furthermore, a review of 706 patients with T2 tumors suggested grade was strongly associated with RCC-specific survival after multivariate analysis (HR 2.27 for Grade 3 and HR 3.76 for Grade 4) (Klatte et al 2007).

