Higher stage, such as T3b, T3c, and T4, also had a poorer prognosis compared with T3a in large Korean study of 1691 patients with post-nephrectomy RCC (Lee et al. 2009). Five-year RCC-specific survival was 62.6% for T3a compared with 41.1%, 50%, and 26% for T3b, T3c, and T4, respectively (see Figure 4). Regional node involvement was also a strong predictor for RCC-specific mortality in this study with a 5-year RCC-specific survival of approximately 33% with nodal involvement.

Figure 4 Renal Cell Carcinoma-Specific Survival According to the 2009 Tumor Node Metastasis Classification

Source: Lee et al. 2009.

Specifically within the T3a stage, in an MD Anderson study of 365 patients with T3a disease, only grade (HR 1.5) and sarcomatoid status (HR 1.8) predicted RCC-specific mortality in a multifactorial analysis (Margulis et al. 2007). Patients who had regional lymph node involvement (HR=2.7 in a unifactorial analysis) also had a poorer prognosis.

Given the potential discrepancies in Fuhrman grading that have been described between local sites and a central review (Aydin et al. 2010) and the importance of grading for eligibility, monitoring of tumor samples for Fuhrman grading will be performed by a central laboratory.

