3.3.2.2 Inclusion of Patients Who Have Undergone Metastasectomy

This study will include patients who have undergone complete metastasectomy to NED (no evidence of disease; R0 resection) status because this population is at very high risk of disease recurrence and therefore represents a high unmet medical need.

Most patients who undergo metastasectomy experience a recurrence, but there is a subset of patients that experiences long-term survival (Eggner et al. 2008;

Dabestani et al. 2014). In a study of 44 patients who underwent complete metastasectomy across diverse sites of metastasis, the 5-year survival rate was 49% (95% CI: 32% to 64%) for all patients and 71% (95% CI: 43 to 87) in the favorable risk group (Eggerer et al. 2008). In a recent series of 138 patients who underwent metastasectomy, the most common sites for resection were lung (57%) followed by adrenal gland (20%) (Untch et al. 2016).

Five-year survival rates in patients with RCC with pulmonary metastases range from 21% to 60% following complete metastasectomy (Meimarakis et al. 2011; Dabestani et al. 2014). The lung is the most common site of recurrence, occurring in about 50% of RCC patients with metastatic disease (Meimarakis et al. 2011). These patients remain at high risk for disease recurrence and death with a 5-year DFS and OS of approximately 33% and 40% in one series that examined patients who underwent complete synchronous or metachronous pulmonary metastasectomy (Hofmann et al. 2005). In the study, patients with synchronous lung lesions who underwent complete resection had a 5-year OS of 0% (n= 5), compared with patients with metachronous resected lung lesions who had a 5-year OS of 43.7% (n=49). In one of the largest studies of pulmonary metastasectomy (n=202), the 5-year OS was 45% following complete (R0) metastasectomy (Meimarakis et al. 2011). Synchronous metastasis was again associated with a worse survival than metachronous metastasis (HR 1.9 [95% CI: 1.2 to 3.0]).

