6.4.1 Primary Efficacy Endpoint: Investigator-Assessed Disease-Free Survival

The primary efficacy endpoint is *investigator*-assessed DFS, defined as the time from randomization to *death from any cause or the first documented recurrence assessed by investigator, whichever occurs first*. Recurrence is defined as any of the following: local recurrence of RCC, new primary RCC and distant metastasis of RCC.

Data for patients without an *investigator*-assessed DFS event will be censored at the last date the patient was assessed to be alive and *investigator*-assessed recurrence free (or, for patients with no post-baseline disease assessment, at the randomization date).

Appropriate sensitivity analyses will be conducted for *investigator*-assessed DFS.

For U.S. registration purposes, the primary efficacy endpoint of *investigator*-assessed DFS will be defined as described above with an additional censoring rule for missed visits. Data for patients with an *investigator*-assessed DFS event who missed two or more scheduled assessments immediately prior to the *investigator*-assessed DFS event will be censored at the last tumor assessment prior to the missed visits.

The following analyses will be performed for both DFS endpoints described above. DFS will be compared between treatment arms using the stratified log-rank test. The hazard ratio (HR) for recurrence or death will be estimated using a stratified Cox proportional hazards model, and the 95% CI for the HR will be provided. The stratification factors will be the same as the randomization stratification factors; however, levels of stratification factors may be combined for analysis purposes if necessary to minimize small stratum cell sizes. Combination of the levels of stratification factors, if any, will be pre-specified in the Statistical Analysis Plan (SAP) prior to data base lock. The stratification factors will be obtained from the IxRS. Results from an unstratified analysis will also be provided.

Kaplan-Meier methodology will be used to estimate for each treatment arm the *investigator-assessed* DFS rate at specific timepoints (e.g., every 6 months or yearly) and to estimate median DFS; Kaplan-Meier curves will be produced.

Brookmeyer-Crowley methodology (Brookmeyer and Crowley 1982) will be used to construct the 95% CI for the median DFS for each treatment arm.

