1. INTRODUCTION

This Statistical Analysis Plan (SAP) describes the analyses that are planned to be performed for the Clinical Study Report (CSR) of WO39210 (IMmotion010). Detailed background information of the study can be found in the [study protocol](#). The analyses described in this SAP will supersede those specified in Protocol WO39210 for the purposes of a regulatory filing.

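### If sparse strata remain after region is dropped, SAP 5.3.2 may delete disease stage outright; combining two stage levels first, only in that case, is a free improvement with a small, conditional gain

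*SAP*

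**What the plan says.** Randomisation is stratified by disease stage (three levels: T2/T3a; T3b/c/T4/N+; resected metastasis), region (two levels) and PD-L1 (IC0 against IC1/2/3) (SAP 1.2.1). The primary analysis starts from the same factors, that is, 12 strata.

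SAP 5.3.2 reduces them if any stratum has fewer than 20 events. In the first step "the geographic region will be removed as a factor in the model given its limited prognostic significance". If a stratum is still short, then "the stratification factor that contains the level with the smallest number of patients will be removed from the stratified analysis". No step combines levels. The trigger counts events, whereas the choice of factor counts patients.

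Protocol 6.4.1 describes a different device: "levels of stratification factors may be combined for analysis purposes if necessary to minimize small stratum cell sizes". It leaves the details to the SAP, to be fixed before database lock. SAP 1 adds: "The analyses described in this SAP will supersede those specified in Protocol WO39210 for the purposes of a regulatory filing". SAP 5.4.1 uses the primary-endpoint methods for OS. SAP Appendix 1 lists no changes from the protocol's analyses.

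**The concern.** The SAP justifies removing region by its weak link with prognosis, but prognosis plays no part in the second step. The factor with the smallest level goes, and a three-level factor is more exposed to that than a two-level one. The protocol presents stage as prognostic: in Protocol 3.3.2.1, "Higher stage, such as T3b, T3c, and T4, also had a poorer prognosis compared with T3a", and Protocol 3.3.4 places patients after complete metastasectomy at very high risk of recurrence. The rule could therefore discard all stage information to cure one thin cell, when pooling two of the three levels would often be enough.

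At stake is some efficiency. Leaving out a prognostic factor that was used in randomisation makes the log-rank test slightly conservative and pulls the estimated hazard ratio slightly toward 1.

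**Working it through.** **The plan's own figure.** Schoenfeld's formula with HR 0.70, two-sided alpha 0.05 and 90% power gives 4 × (1.960 + 1.282)² / (ln 0.70)² = 331 events; Freedman's gives 338. The stated 334 events give 90.3% power. The critical hazard ratio is exp(−1.96 × 2/√334) = 0.807, against the stated 0.80. SAP 3.2 sizes the trial on a log-rank test and takes no credit for stratification.

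**Which factor goes.** The smallest of three stage levels cannot exceed one third of patients. If the smaller PD-L1 class exceeds one third, stage is removed by arithmetic. Below one third, it depends on the actual level sizes. The only split in the documents is Protocol 1.3.2.2, Table 3: 22 IC0 and 33 IC1/2/3, so 22/55 = 40% IC0 (Wilson 95% interval 28% to 53%), in a metastatic cohort. The rule "The highest PD-L1 staining score will be used for patients who provide both nephrectomy and metastasectomy specimens" (Protocol synopsis) can only lower the IC0 share.

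**When the second step fires.** Mean events per stratum for DFS are 334/12 = 27.8, then 334/6 = 55.7 without region, and 334/4 = 83.5 with two stage levels. Assume a 40% smaller PD-L1 class, independent of stage. The resected-metastasis level then needs 20/0.40 = 50 events for its smaller cell to reach 20. That is 15% of 334 DFS events, but 26%, 23% and 20% of 190, 222 and 254 deaths.

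A grid of 700 assumed combinations (resected metastasis 5–25% of patients, IC1/2/3 30–70%, stage hazard ratios 1–2.5) gives, on expected events:

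| Analysis | Second step fires | Factor removed is stage | Combining the two higher-risk levels clears 20 per stratum |
|---|---|---|---|
| DFS, 334 | 56% | 100% | 99.5% |
| OS, 254 | 77% | 100% | 93% |
| OS, 222 | 85% | 100% | 86% |
| OS, 190 | 93% | 100% | 77% |

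The last two columns are percentages of the combinations in which the step fires. The rate depends strongly on the metastasis share. In simulation at a 40% PD-L1 split, stage is lost for DFS in 91–100% of trials at an 8% share, 62–95% at 10%, 5–45% at 15% and 0–36% at 20%. At 190 deaths the ranges are 100%, 100%, 85–100% and 47–100%.

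**How prognostic stage may be.** Five-year RCC-specific survival in Protocol 3.3.2.1 gives hazard ratios against T3a of ln 0.411/ln 0.626 = 1.90 (T3b), ln 0.50/ln 0.626 = 1.48 (T3c) and ln 0.26/ln 0.626 = 2.88 (T4). For resected metastasis, Protocol 3.3.2.2 reports that "the 5-year OS was 45% following complete (R0) metastasectomy"; ln 0.45/ln 0.626 = 1.70. This last ratio is rough, because it sets overall survival in one study against RCC-specific survival in another. The contrast in this trial may also be smaller: T3a enters only with Grade 3–4 and T2 only with Grade 4, and "In an Italian study of 338 patients with T3 and T4 tumors, grade was strongly associated with RCC-specific survival".

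**Cost of deleting stage (DFS).** Simulation of 4,000 trials per row, 764 patients, true HR 0.70, stage shares 60/30/10%:

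| Stage hazards | Power, PD-L1 only | Power, combined stage × PD-L1 | Estimated HR |
|---|---|---|---|
| 1/1/1 | 90.2% | 90.0% | 0.700 vs 0.700 |
| 1/1.5/1.5 | 89.7% | 90.0% | 0.703 vs 0.700 |
| 1/1.9/2.0 | 89.8% | 90.7% | 0.708 vs 0.700 |
| 1/1.9/3.0 | 87.5% | 89.2% | 0.713 vs 0.703 |

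Under the null, the rejection rate was 4.6% with PD-L1 only and 5.1% with combined stage (simulation SE 0.3 points).

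**Gain from the limited fix.** At a 40% PD-L1 split with 10% resected metastasis (2,500 paired trials per setting), it is about 0.5–1.2 points for DFS and 0.7–2.4 points for OS at 190 deaths.

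**Why the limited fix cannot give a coarser analysis.** There are four cases. If the second step does not fire, nothing changes. If PD-L1 is the factor to be removed, nothing changes. If stage is to be removed and the combined strata all reach 20, the analysis uses two stage levels by PD-L1 instead of PD-L1 alone. If they do not, the SAP rule applies.

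**The case against.** The current rule is objective, fully pre-specified and accompanied by an unstratified analysis. A reader might infer that it breaches the protocol. It does not: Protocol 6.4.1 only permits combining levels, and SAP 1 gives the SAP precedence. A reader might also infer that stage will be lost and the 90% power with it. The documents give no level sizes, so the first is unknown, and the planned power never relied on stratification. These objections stand.

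It is also tempting to combine the stage levels whenever a stratum is sparse, before any factor is considered for removal. That is not free. With a PD-L1 split near 10% and stage hazards 1/1/2, the current rule drops PD-L1 and keeps all three stage levels, whereas an automatic merge loses about 1 point of power. At a 20% split and 190 deaths, it raises the chance that PD-L1 is dropped from about 6% to about 87%. This objection is decisive against an unconditional merge, but it does not reach a merge limited to cases where stage would be deleted.

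Protocol 3.3.4 notes that metastasectomy patients may fare differently from those without metastasis, so the choice of pair is open to debate. But the alternative in those cases is PD-L1 alone, which pools all three levels.

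Finally, counting deaths for OS is the natural reading of SAP 5.4.1, so stating it is only a clarification.

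**Conclusion.** This is a free improvement, not an error. If a sparse stratum remains after region is dropped, SAP 5.3.2 removes a whole factor by patient count. That factor is stage whenever the smallest stage level is smaller than the smaller PD-L1 class. How often this would happen is unknown; it is more likely for OS than for DFS.

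Under the assumed shares, losing stage costs about 0 to 2.5 power points. With weak stage contrasts (hazards 1/1.2/1.5), or if only resected metastasis differs (1/1/2), the difference from combining was nil (−0.2 to +0.1 points) at the splits simulated. The fix also has limited reach when PD-L1 is lopsided: at a 20% split, a combined stratum was still short in about 15% of DFS analyses and 90% of OS analyses at 190 deaths, and the SAP rule would then apply.

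All of this rests on assumed stratum shares and stage hazards. The structural statements do not: which factor is removed, and that the limited change is never coarser than the SAP's analysis.

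**What to change.** Amend the second step of SAP 5.3.2 to read:

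> If the factor to be removed is disease stage, the T3b/c/T4/N+ and resected-metastasis levels are first combined. If every combined-stage × PD-L1 stratum then has at least 20 events, the analysis is stratified by combined stage and PD-L1. Otherwise, or if the factor to be removed is PD-L1, the factor is removed as now stated. Events are those of the endpoint being analysed.

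An entry in SAP Appendix 1 is optional, because Protocol 6.4.1 is permissive and the SAP takes precedence. The cost is four sentences, with no extra patients, data or analyses. The event counts can be pooled over arms, so the change can be made blinded, before database lock.

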5.3.3 Sensitivity Analyses for Primary Endpoint(s)

5.3.3.1 Sensitivity Analyses for Impacts of Missed Visits

For U.S. registration purposes, the impact of missed visits on investigator-assessed DFS will be assessed. The investigator-assessed DFS will be defined as described in Section 5.3.1 with an additional censoring rule for missed visits. Data for patients with an investigator-assessed DFS event who missed two or more scheduled assessments immediately prior to the investigator-assessed DFS event will be censored at the last

tumor assessment prior to the missed visits. Methods for comparison between treatment arms will be the same as the methods for treatment comparison for the primary endpoint of investigator-assessed DFS.

5.4 SECONDARY ENDPOINT ANALYSES

5.4.1 Overall Survival

OS (the key secondary efficacy endpoint) is defined as the time from randomization to death from any cause. Data for patients who have not died will be censored at the last date known to be alive or at the randomization date for patients with no post baseline information. Statistical hypothesis which will be tested for OS is given in Section 2. Methods for comparison of OS between treatment arms will be the same as the methods for treatment comparison for the primary endpoint of investigator-assessed DFS.

5.4.1.1 Sensitivity Analyses for Impact of Patients in Placebo Arm Receiving Atezolizumab or Similar Immunotherapy

The impact on OS of patients in the placebo arm subsequently receiving atezolizumab or another immunotherapy considered similar to atezolizumab in its mechanism of action may be assessed, depending on the number of such patients. If more than 5% of patients in the placebo arm have received atezolizumab or a similar immunotherapy, the following analyses may be performed to compare treatment arms at each of the interim analyses and the OS final analysis, as applicable:

- OS in the placebo arm will be discounted according to a range of possible effects on OS after having received atezolizumab or another immunotherapy (e.g., 10%, 20%, 30%, etc.).
- Additional sensitivity analyses may be conducted if deemed necessary.

